**Table 11: AG-120 and AG-221 Hematologic and Non-hematologic Toxicity Dose Levels**

Dose Level	IDH1	IDH2
	AG-120	AG-221
-1	250 mg QD	50 mg QD
1	500 mg QD	100 mg QD
2	NA	200 mg QD

**Dose escalation for augmenting treatment responses**

If during the Phase 1b segment of this study the 200 mg dose is confirmed by the DRT as safe, the AG-221 dose may be escalated for the subsequent treatment cycles from 100 mg QD to 200 mg QD if the following occurs:

- no partial remission (PR) is achieved after treatment with AG-221 for at least 2 cycles without  $\geq$  Grade 3 AEs suspected by the investigator to be related to AG-221; or
- no complete remission (CR) is achieved after treatment with AG-221 for at least 4 cycles without  $\geq$  Grade 3 AEs suspected by the investigator to be related to AG-221; or
- evidence of morphologic relapse or progression of disease.

If benefit is demonstrated at an increased level of dose, then that dose level should be maintained during the subsequent treatment cycles that are given. However, once increased, the AG-221 dose may be reduced if a certain level of toxicity (see Section 7.2.2.3.2) is observed and is considered as possibly or probably related to AG-221 treatment. Only one dose escalation will be allowed, and the AG-221 dose cannot be re-escalated more than once.

**7.2.2.3.2. Toxicities During AG-120 or AG-221 Treatment**

**Hematologic toxicities**

Hematologic toxicities of cytopenias ( $> 50\%$  decrease from baseline [Day 1 of Cycle 1]) and/or marrow cellularity  $< 5\%$  on Day 28 of a cycle or later without evidence of leukemia.

Prolonged hematologic toxicities during study treatment should result in a discussion between the investigator and the medical monitor.

**Non-hematologic toxicities**

Non-hematologic toxicities include all clinically significant non-hematologic toxicities of  $\geq$  Grade 3 with the exception of  $\geq$  Grade 3 blood bilirubin increases in subjects with a UGT1A1 mutation. In subjects with a UGT1A1 mutation, blood bilirubin increases of  $> 5 \times$  ULN may be considered clinically significant.

QT prolongation

The discussion of the emergency management of torsade de pointes and its hemodynamic consequences is beyond the scope of this guideline.

[REDACTED] As of 01 May 2015, 6 (10.5%) of 57 subjects in Study AG120 C 001 have experienced QT prolongation while receiving AG 120. QTc interval has been observed in dogs at relatively low doses of AG-221. Prolonged QTc interval has not been seen in other animal species at high doses.

Subjects may be at increased risk for the development of QT prolongation when treated with AG 120 administered with fluoroquinolones, azole antifungal agents, or serotonin (5-HT3) antagonists. Investigators need to be vigilant; refrain from administering concomitant medications associated with QT prolongation, and if no other therapeutic options are available, monitor subjects receiving AG-120 with the combination of these drugs, and evaluate ECG and electrolytes (including potassium, magnesium, and calcium) particularly in subjects presenting with nausea, vomiting, or diarrhea.

Please refer to the [AG-120 Investigator's Brochure](#) for detailed information concerning the available pharmacology, toxicology, drug metabolism, clinical studies, and adverse event profile of AG-120.

Subjects who experience prolongation of the heart-rate corrected QT interval, Fridericia's correction (QTcF) to > 480 msec (Grade  $\geq$  2) while treated with AG-120 or AG-221, should be promptly evaluated for causality of the QTc prolongation and managed according to the following guidelines:

- Levels of electrolytes (potassium, calcium, and magnesium) should be checked and supplementation given to correct any values outside the normal range.
- Concomitant therapies should be reviewed and adjusted as appropriate for medication with known QT prolonging effects.
- If no other cause is identified and the investigator believes it is appropriate, particularly if QTc remains elevated (after above measures have been implemented, or as determined by the investigator), investigational product may be interrupted, and an ECG should be rechecked in approximately 1 week after the QTc prolongation was first observed, or more frequently as clinically indicated.
  - If QTc has recovered or improved and the investigator believes it is safe to do so, re-challenge with AG-120 or AG-221 should be considered if held. ECGs should be conducted at least weekly (eg, at every scheduled visit) for 2 weeks following QTc reduction  $\leq$  480 msec.
  - If Grade 2 (QTcF > 480 and  $\leq$  500 msec), the dose of AG-120 or AG-221 may be reduced to a dose approved by the medical monitor without interruption of dosing. The AG-120 or AG-221 dose may be re-escalated to the prior dose in  $\geq$  14 days after QT prolongation has decreased to  $\leq$  Grade 1.
  - If Grade 3 (QTcF > 500 msec), when QTc prolongation is first observed, hospitalization for continuous cardiac monitoring and evaluation by a cardiologist should both be considered. Dosing with AG-120 or AG-221 will be interrupted. If QTc returns to within 30 ms of baseline or < 450 msec within 14 days, treatment may be resumed at a reduced dose. The AG-120 or AG-221 dose cannot be re-escalated following dose reduction for Grade 3 QTcF prolongation

unless the prolongation was associated with an electrolyte abnormality or concomitant medication.

- If Grade 4 (QTcF > 500 msec or > 60 msec change from baseline with torsade de pointes or polymorphic ventricular tachycardia or signs/symptoms of serious arrhythmia), subjects should be admitted to hospital when QTc prolongation is first observed for continuous cardiac monitoring and be discharged only after review by a cardiologist. Dosing with AG-120 or AG-221 should be permanently discontinued.

### IDH Differentiation Syndrome

Subjects treated with AG-120 or AG-221 may develop signs and symptoms of a IDH Differentiation Syndrome. Signs and symptoms could include fever, dyspnea, edema/ weight gain, increased serum creatinine and, in some cases, clinical features consistent with the acute respiratory distress syndrome with associated pulmonary infiltrates, and pulmonary or pericardial effusions. Increases in white blood cell (WBC) count concurrent to Differentiation Syndrome has been observed, but by itself do not substantiate the syndrome. No single sign or symptom may be considered per se as diagnostic of the syndrome.

Corticosteroids should be promptly initiated at a suggested dose 10 mg of dexamethasone IV every 12 hours until resolution of IDH Differentiation Syndrome, after which the dose can be progressively reduced in the next few days or weeks.

Further information on diagnosis and treatment of IDH Differentiation Syndrome can be found in the supplemental guidance document.

### Leukocytosis

Initiation of treatment with the differentiating agents may lead to rapid WBC expansion not associated with infectious process and not manifesting with the signs and symptoms of IDH Differentiation Syndrome discussed above.

In subjects with elevated WBC, prompt initiation of hydroxyurea is suggested, as per standard local practices (eg, dose of 2 to 3 g PO twice or three times daily for WBC > 30 x 10^9/L). In case of severe leukocytosis (WBC >100 x 10^9/L), use of leukapheresis may be appropriate. Subject should be regularly monitored for changes in WBC count and for new signs and symptoms of infection or IDH Differentiation Syndrome.

### Gastrointestinal Disorders

Appropriate monitoring and timely management of gastrointestinal toxicities, as appropriate, is critical in avoiding malnourishment and dehydration.

### Abnormal Level of Liver Enzymes

Subjects with elevations in ALT  $\geq$  3-fold ULN, subjects will be monitored using the algorithm:

- Repeat LFT (ie, ALT, AST, total bilirubin, ALP, GGT) within < 3 days of the initial test. FU 2-3 times weekly, and weekly when stable
- Perform additional diagnostic follow up:

- Focused medical history, including review of prior history of liver or biliary disorders, concurrent symptoms, review of all concomitant medications [eg, acetaminophen-containing medications, over-the-counter or herbal medications, nutritional supplements] including any changes in medications, detailed review of alcohol use
- Hepatitis serology (anti-HAV, HBsAg, anti-HBs, anti-HB core, anti-HCV, HCV RNA, EBV and CMV screen), and autoantibodies (eg, ANA, anti-smooth muscle antibody)
- Complete physical examination
- Liver ultrasound and follow-up imaging as appropriate
- Additional evaluation as appropriate (INR, PT)

#### **7.2.2.3.3. Initiation of Each AG-120 or AG-221 Treatment Cycle**

In order to proceed to the next AG-120 or AG-221 treatment cycle, subjects must continue to meet entry level values regarding renal and hepatic function (see Section 4.2).

In addition, hematologic recovery is defined as an increase of cell line(s) where hematological toxicity was observed of at least half of the difference of nadir and the baseline count plus the nadir count (ie, blood count at recovery  $\geq$  Nadir Count + (0.5 x [Baseline count – Nadir count])). If the subject does not meet these criteria, the start of the next cycle will be delayed. If the hematologic toxicity is attributed solely to the administration of azacitidine, AG-120 or AG-221 may continue to be given daily until recovery of counts as described below in Section 7.2.2.3.4. The initiation of a new cycle will start upon the ability to reinitiate the combination therapy. If there is a delay of more than 28 days (4 weeks) in the start of the next treatment cycle, the medical monitor should be consulted for the risks and benefits of continuing AG-120 or AG-221 or combination treatment. Subjects who experience persistent Grade  $\geq$  3 toxicity that are assessed as possibly or probably related to AG-120 or AG-221 treatment may continue AG-120 or AG-221 treatment if, in the opinion of the investigator and the medical monitor, the subject is experiencing clinical benefit from AG-120 or AG-221 treatment.

The initiation of a new cycles will start upon the administration of the 7 day of SC azacitidine.

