**Table 12: Hematologic Dose Reductions Based on ANC and Platelets**

Nadir Counts		% Dose in the next course if recovery a is not achieved in next 14 days
ANC (x10  /L)	Platelets (x10  /L)	
≤ 1.0	≤ 50.0	50%
> 1.0	> 50.0	100%

a Recovery = counts  $\geq$  nadir count + (0.5 x [baseline count – nadir count])

**Subjects with reduced baseline blood counts (ie, WBC count  $< 3.0 \times 10^9/L$  or ANC  $< 1.5 \times 10^9/L$  or platelets  $< 75.0 \times 10^9/L$ ) prior to treatment**

Following azacitidine treatment, if the decrease in WBCs or ANC or platelets from that prior to treatment is less than 50%, or greater than 50% but with an improvement in any cell line differentiation, the next cycle should not be delayed and no dose adjustment made.

If the decrease in WBC or ANC or platelets is greater than 50% from that prior to treatment, with no improvement in cell line differentiation, the next cycle of azacitidine therapy should be delayed until the platelet count and the ANC have recovered. If recovery is achieved within 14 days, no dose adjustment is necessary. However, if recovery has not been achieved within 14 days, bone marrow cellularity should be determined. If the bone marrow cellularity is  $> 50\%$ , no dose adjustments should be made. If bone marrow cellularity is  $\leq 50\%$ , treatment should be delayed and the dose reduced according to the following table:

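### For a combination subject with low baseline counts, a fall above 50% and improving differentiation, Protocol 7.2.2.3.3 delays the next cycle and 7.2.2.3.4 says not to; in Phase 2 only Arm 1 is under both rules

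*Protocol*

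**What the plan says.** Four parts of the protocol bear on when a combination subject starts the next cycle.

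- **Section 7.2.2.3.2, hematologic toxicities.** A cytopenia counts as hematologic toxicity when it is a fall of more than 50%: "decrease from baseline [Day 1 of Cycle 1]) and/or marrow cellularity" below 5%. The sentence ends with a qualifier, Day 28 or later and no evidence of leukemia. It is unclear whether this covers the cytopenia or only the marrow finding.
- **Section 7.2.2.3.3, cycle initiation.** It opens "In order to proceed to the next AG-120 or AG-221 treatment cycle", requires entry-level renal and hepatic values, and adds that "hematologic recovery is defined as an increase of cell line(s) where hematological toxicity was observed of at least half of the difference of nadir" and baseline, plus the nadir. Then: "If the subject does not meet these criteria, the start of the next cycle will be delayed". It makes no exception for reduced baseline counts or improving differentiation. It also says: "The initiation of a new cycle will start upon the ability to reinitiate the combination therapy".
- **Section 7.2.2.3.4, subjects with reduced baseline counts** (WBC below 3.0, ANC below 1.5 or platelets below 75 x10^9/L). If the fall is "greater than 50% but with an improvement in any cell line differentiation, the next cycle should not be delayed and no dose adjustment made".
- **Definition of a new cycle.** Section 7.2.2.3.3 ties it to the 7-day azacitidine course. Section 7.2.2.3.4 generally ties it to azacitidine Day 1.

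In Phase 2, Arm 1 receives AG-221 + azacitidine and Arm 2 azacitidine alone, with the same planned azacitidine regimen. All Phase 1b AG-120 and AG-221 cohorts also receive azacitidine.

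**The concern.** The two sections give opposite instructions for the same subject on the same day. They do not run on separate clocks, because each starts the new cycle with azacitidine. A site cannot follow both, and no order of precedence is stated.

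This matters beyond site conduct because the randomized question is what AG-221 adds to azacitidine. Arm 2 takes no inhibitor, so 7.2.2.3.3 does not apply to it. If sites apply that section in Arm 1, azacitidine could be given less often in Arm 1 than in Arm 2 for identical counts. The contrast would then mix the effect of AG-221 with a difference in azacitidine delivery.

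**Working it through.** The plan states no figure on this point, so there is none to reproduce. The check has three steps.

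**1. Can a count still more than 50% below baseline satisfy 7.2.2.3.3?** Let B be the baseline and N the nadir. The threshold in 7.2.2.3.3 is

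T = N + 0.5 x (B - N) = 0.5B + 0.5N.

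Since N is not negative, T is never below 0.5B. A count still more than 50% below baseline therefore always fails. A grid over nadirs and counts below 0.5B found no exception. By depth of the nadir:

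| Fall at nadir | Nadir | Threshold T |
|---|---|---|
| 55% | 0.45B | 0.725B |
| 60% | 0.40B | 0.70B |
| 70% | 0.30B | 0.65B |
| 80% | 0.20B | 0.60B |
| 90% | 0.10B | 0.55B |

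**2. One subject under both rules.** Take baseline ANC 1.0 (reduced, being below 1.5), nadir 0.3 and a Day 28 value of 0.45 x10^9/L, with improving differentiation and no evidence of leukemia. The Day 28 fall is 1 - 0.45/1.0 = 55%, so the toxicity definition is met whichever way the Day 28 and leukemia qualifier is read.

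- Section 7.2.2.3.3: T = 0.3 + 0.5 x (1.0 - 0.3) = 0.65. Since 0.45 < 0.65, the next cycle is delayed.
- Section 7.2.2.3.4: reduced baseline, fall above 50%, improving differentiation. The next cycle is not delayed and the dose is unchanged.

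Had the count regained 0.65 by the planned start, the sections would agree.

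**3. What a delay would do to azacitidine dose intensity.** The planned dose is 75 mg/m2/day for 7 days of each 28-day cycle: 7 x 75 / 28 = 525 / 28 = 18.75 mg/m2/day, as in SAP 9.4. The documents give no delay frequency or length, so these are assumptions showing a range:

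- 14-day delay in every cycle: 525 / 42 = 12.5 mg/m2/day, and 12.5 / 18.75 = 67%.
- 14-day delay in half of cycles: mean cycle (28 + 42) / 2 = 35 days, 525 / 35 = 15 mg/m2/day, and 15 / 18.75 = 80%.
- No delay: 18.75 mg/m2/day, 100%.

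These are long-run values for an affected subject. SAP 9.3 credits the last cycle with 28 days, so an observed figure is somewhat higher. With six cycles and a delay before each of the five later ones, it is 6 x 525 / (5 x 42 + 28) = 3150 / 238 = 13.2 mg/m2/day, or 71%.

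**The case against.** The strongest reply is that 7.2.2.3.3 already points to the azacitidine rules: "If the hematologic toxicity is attributed solely to the administration of azacitidine, AG-120 or AG-221 may continue to be given daily until recovery of counts", with a reference to 7.2.2.3.4. Section 3.1.1.3 says the inhibitors are not associated with myelosuppression. A site might therefore treat such cytopenias as azacitidine's and let the reduced-baseline rule decide. That reading is reasonable, but the text does not secure it. The sentence lets the inhibitor continue, and the next one still holds the new cycle until the combination can be restarted.

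Other limits do stand:

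- If the no-leukemia qualifier in 7.2.2.3.2 covers the cytopenia, subjects with persisting leukemia do not trigger the delay. Subjects enter with at least 20% marrow blasts, so this could exclude a sizeable group.
- Arm 2 subjects with reduced baseline counts, a fall above 50% and no improvement in differentiation are also delayed to the same recovery formula. The arms diverge only in the differentiation branch.
- The SAP already summarizes average cycle length, azacitidine dose intensity and relative dose intensity categories by arm (SAP 9 to 9.4).
- The latest amendment justification says the primary analysis report was finalized, with 15 subjects left on treatment, all on a combination. Rewording cannot change azacitidine delivery in data already analyzed.

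A reader might also infer a second conflict, because 7.2.2.3.4 makes no dose adjustment when marrow cellularity exceeds 50% after 14 days without recovery. The text does not show one. That clause concerns dose; the same paragraph has already delayed the cycle until recovery, and the clause does not say the delay is lifted. The Appendix J flow diagram, which might settle this, is not in the text available here.

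**Conclusion.** The contradiction is real and narrow. It needs a combination subject with reduced baseline counts, a fall above 50%, improving differentiation and a count below the recovery threshold at the planned cycle start. On one reading of 7.2.2.3.2 it also needs no evidence of leukemia. Under those conditions 7.2.2.3.3 delays, 7.2.2.3.4 does not, and neither prevails.

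Within Phase 2 only Arm 1 is under both rules. It would be wrong to conclude that AG-221 subjects alone are affected across the study: 7.2.2.3.3 names AG-120 equally, and all Phase 1b combination subjects receive azacitidine.

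The effect on the randomized comparison is possible but unmeasured. The 67% and 80% figures rest on an assumed 14-day delay in every cycle or in half of cycles. A reader might take them as a forecast for Arm 1, but the documents do not say how many subjects meet the conditions or how long they would wait. The leukocytosis paragraph of 7.2.2.3.2 refers to the inhibitors as agents that drive differentiation, so the branch may arise more often in Arm 1. That is plausible from one phrase and no more.

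**What to change.** Reconcile 7.2.2.3.2, 7.2.2.3.3 and the reduced-baseline rules of 7.2.2.3.4 so that one stated hematologic condition decides when a combination subject starts the next cycle. Say whether the Day 28 and no-leukemia qualifier applies to cytopenias, and whether the condition is meant to match the control arm. This review takes no view on which rule is clinically right.

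In the SAP, add cycle delays by arm, and split the planned cycle-length and azacitidine dose-intensity summaries by baseline-count group (reduced or not). For the comparison already analyzed, this reporting is the useful part, since it would show whether azacitidine delivery differed between the arms.

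The cost is protocol wording, one site clarification for the remaining combination subjects, and one SAP table. No new data collection appears necessary, since baseline counts, visit dates and dosing records are already captured.

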#### **7.2.2.3.4. Dose Modifications Guidelines for Azacitidine**

The first treatment cycle of azacitidine should always be given at 100% of the dose, regardless of the subject's laboratory values (provided that the subject is allowed to enroll in the study based on the inclusion and exclusion criteria).

Subjects should be monitored for hematologic toxicity and renal toxicity; a delay in starting the next treatment cycle or dose reduction as described by the guidance below. Azacitidine dose level modifications should be made taking the subjects clinical situation including previous adverse events (e.g. bleeding or infections) and the status of the subjects disease into account. If the dose of azacitidine is modified during the course of the study (see below) and benefit is demonstrated at the reduced dose, that dose should be maintained during subsequent cycles (unless toxicity develops). The investigator should contact the medical monitor for guidance on azacitidine dose modification, if needed.

Cycle length is 28 days unless a delay for toxicity/AE is encountered. Generally, the initiation of a new cycle will be defined as Day 1 of the azacitidine administration or Day 29 of the AG120/AG221 administration in case azacitidine has been permanently discontinued.

**Azacitidine Dose Modifications due to Nonhematological Toxicity**

Following receipt of any dose of azacitidine, subsequent treatment cycles may be delayed if a certain level of toxicity occurs after the previous dose. Any subject who experiences a non-hematological AE of Grade 3 or 4 that is an escalation from his or her status at baseline (Section 6.2.1) should have azacitidine temporarily discontinued until the toxicity Grade returns to less than Grade 3. Azacitidine should be permanently discontinued if the non-hematological toxicity persists as Grade 3 or 4 for more than 21 days, despite the temporary interruption of azacitidine.

Necrotising fasciitis, including fatal cases, have been reported in patients treated with azacitidine. Azacitidine therapy should be discontinued in patients who develop necrotising fasciitis, and appropriate treatment should be promptly initiated.

If azacitidine is permanently discontinued in the combination arms, AG-120 or AG-221 may continue at the discretion of the investigator.

**Dose Modifications Due to Hematological Toxicity**

Treatment with azacitidine is associated with anemia, neutropenia and thrombocytopenia, particularly during the first 2 cycles. Complete blood counts should be performed as specified in Table 4: Table of Events, and as needed to monitor toxicity.

Recovery is defined as an increase of cell line(s) where hematological toxicity was observed of at least half of the difference of nadir and the baseline count plus the nadir count (ie, blood count at recovery  $\geq$  Nadir Count + (0.5 x [Baseline count – Nadir count])).

**Subjects without reduced baseline blood counts (ie, white blood count [WBC]  $\geq$  3.0 x 10^9/L, ANC  $\geq$  1.5 x 10^9/L, and platelets  $\geq$  75.0 x 10^9/L) prior to first treatment**

If hematological toxicity is observed following azacitidine treatment, the next cycle of azacitidine therapy should be delayed until the platelet count and the absolute neutrophil count have recovered. If recovery is achieved within 14 days, no dose adjustment is necessary. However, if recovery has not been achieved within 14 days, the dose should be reduced according to the following table. Following dose modifications, the cycle duration should return to 28 days. The reduced dose should be maintained during subsequent cycles that are given (unless toxicity develops). A flow diagram for the determination of azacitidine dose adjustment in subjects without reduced baseline blood counts is provided in Appendix I.

